### **6.3.3. Analysis Methods**

The main analysis of categorical efficacy variables and health outcomes variables will use a logistic regression analysis with treatment group in the model. The p-value and 100(1-alpha)% CI for the odds ratio from the logistic regression model are used for primary statistical inference. The difference in percentages and 100(1-alpha)% CI of the difference in percentages using the Newcombe-Wilson without continuity correction will be reported. The p-value from the Fisher's exact test will also be produced as a secondary analysis.

The main analysis for all continuous efficacy and health outcomes variables will use mixed model repeated measures (MMRM) analysis. The model will include treatment, region, baseline disease severity, visit, and treatment-by-visit-interaction as fixed categorical effects and baseline and baseline-by-visit-interaction as fixed continuous effects. An unstructured (co)variance structure will be used to model the between- and within-patient errors. If this analysis fails to converge, the heterogeneous autoregressive [ARH(1)], followed by the heterogeneous compound symmetry (CSH), followed by the heterogeneous Toeplitz (TOEPH) will be used. The Kenward-Roger method will be used to estimate the degrees of freedom. Type III tests for the least-squares means (LSM) will be used for the statistical comparison. The LSM difference, standard error, p-value and 100(1-alpha)% CI will also be reported.

Fisher's exact test will be used for the adverse events (AEs), discontinuation, and other categorical safety data for between-treatment group comparisons. Continuous vital signs, body weight, and other continuous safety variables, including laboratory variables, will be analyzed by an ANCOVA with treatment group and baseline value in the model. The significance of within-treatment group changes from baseline will be evaluated by testing whether or not the treatment group LSM changes from baseline are different from zero; the standard error for the LSM change will also be displayed. Differences in LSM will be displayed, with the p-value associated with the LSM comparison to placebo and a 95% CI on the LSM difference also provided. In addition to the LSMs for each group, the within-group p-value for the change from baseline will be displayed. Treatment-emergent high/low for categorical laboratory safety analyses will also be produced.

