9.2. Sample Size Determination

Approximately 100 patients will be screened to achieve approximately 63 participants randomized in a 2:1 ratio to one of two treatment groups:

approximately 42 participants randomized to LY3041658, and

approximately 21 participants randomized to placebo.

For all randomized patients, approximately 45 patients are expected to complete the 16 weeks' treatment period. This sample size provides at least 80% power to the primary endpoint of HiSCR response. This calculation is a 2-sided test for superiority of LY3041658 compared to placebo on HiSCR response rate with significance level of 0.05 CCl

CCI

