9.4.6. Other Analyses

Sensitivity Analyses

Fisher's exact test may be used as an alternative to logistic regression on the primary endpoint due to the small sample size for this analysis. Other sensitivity analyses will be considered for the secondary endpoints.

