#### 6.1.1. Estimands

The study will compare LY3041658 with placebo in participants with HS.

The primary comparison of interest is the difference in proportion of participants who achieve HiSCR response at Week 16. The primary objective is to demonstrate superiority of LY3041658 versus placebo.

The primary comparison will be assessed using a composite estimand where the intercurrent events of premature discontinuation and use of prohibited medication are part of the response definition.

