### 6.3. General Considerations

Efficacy analyses will be conducted on the Modified Intent-to-Treat (mITT) and Per-Protocol Set Population. The mITT set includes all data from all randomized participants receiving at least 1 dose of the IP according to the treatment the participants were assigned. The PPS set includes all data from all randomized participants who missed no more than 1 dose of study treatment to which they were assigned up to and including Week 14.

Safety analyses will be conducted on the Safety Population. This set includes all data from all randomized participants receiving at least 1 dose of the IP according to the treatment the participants actually received.

All tests of treatment effects will be conducted at a 2-sided alpha level of 0.05, unless otherwise stated. All confidence intervals (CIs) will be given at a 2-sided 95% level. Descriptive summaries of continuous data will present the group mean, standard deviation, median, minimum, maximum, and sample size. Descriptive summaries of discrete data will report the number of participants and incidence as a frequency and as a percentage. All p-values will be rounded up to 3 decimal places.

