### 6.7.3. Exploratory Endpoints

#### 6.7.3.1. Additional HiSCR Response Definitions

The primary endpoint will be assessed using different definitions of HiSCR response at Week 16. Specifically, the needed reduction in AN count will be modified from 50% to 75% and to 90%. The same analysis method used for the primary endpoint will be used for these exploratory analyses. The percentage of responders achieving, HiSCR50, HiSCR75, and HiSCR90, in the mITT and the PPS population will be summarized by visit and by treatment arm to which the patients were randomized at Week 0 (Visit 2). A plot of the percentage of responders over weeks will be provided.

The proportion of visits that a patient achieves HiSCR response out of the total visits the patient attends during study period 1 and 2 (Week 0 to Week 36) will be calculated as follow,

$$\frac{\text{\# of visits the patient achieves HiSCR response}}{\text{Total \# of visits the patient attends}} * 100.$$

The HiSCR response is defined in Section 6.7.1 which is based on a patient's baseline values. The summary statistics of the proportion of visits achieving responses will be summarized by treatment arms to which the patients were randomized at Week 0 (Visit 2).

Moreover, the restricted mean response time (RMRT), a measure of the average time a responder stays a responder within a specified time period, will be provided up for responders at week 16 up (Visit 10) to week 36 (Visit 20) in each treatment arm, respectively. The time to loss of response in HiSCR50 is defined as  $\geq 50\%$  increase in AN compared to the average AN count from the 3 previous visits, and the increase was  $\geq 3$  AN from the average AN count of the 3 previous visits. Specifically, the RMRT is calculated as,

$$\sum_{k=10}^{20} \left\{ \prod_{v=10}^k \left( 1 - \frac{\delta_v}{R_v} \right) \right\} \times 2 \text{ weeks}$$

Where  $\delta_v$  is the number of patients who are responder at Visit 10 (week 16) but first loss response at Visit  $v$  and  $R_v$  is the number of patients who are responder at Visit 10 (week 16) and stay reponse before Visit  $v$ . The average RMRT will be summarized by treatment arm to which the patients were randomized at Week 0 (Visit 2).

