### **6.10. Subgroup Analyses**

Subgroup analyses comparing LY3041658 to placebo will be performed on the mITT and PPS population at Week 16 for the following:

- Proportion of participants achieving HiSCR response
- Mean change from baseline to Week 16 in:
  - Total number of abscesses and inflammatory nodules (AN count)
  - Skin Pain – HS Numeric Rating Scale (NRS)

The following subgroups (but not necessarily limited to only these) will be categorized into disease-related characteristics and demographic characteristics will be evaluated:

- Gender: (Male; Female)
- Race: (Asian; Black/African American; White; or Other)
- Ethnicity: (Hispanic or Latino; and Not Hispanic or Latino)
- Region: (United States; and Australia)
- Age (<40,40-65,>65)
- Weight (<60kg, >=60 and <100kg, >=100kg)
- BMI (<25 kg/m^2, >=25 and <40 kg/m^2, >=40 kg/m^2)
- Baseline Hurley stage: II, III

Descriptive statistics will be provided for each treatment and stratum of a subgroup as outlined, regardless of sample size. The subgroup analyses for categorical outcomes will be performed using logistic regression. The model will include the categorical outcome as the dependent variable and treatment, subgroup, and treatment-by-subgroup interaction as explanatory variables. Missing data will be imputed using NRI (Section 6.4). The treatment-by-subgroup interaction comparing treatment groups will be tested at the 0.1 significance level. The p-value

from the logistic regression model will be reported for the interaction test. Response counts and percentages will be summarized by treatment for each subgroup category. The difference in percentages and 100(1-alpha)% confidence interval (CI) of the difference in percentages using the Newcombe-Wilson without continuity correction will be reported. The p-value from the Fisher's exact test will also be produced.

Additional subgroup analyses on efficacy may be performed as deemed appropriate and necessary.

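### The logistic test behind the primary HiSCR inference is not named and has no binding rule for an arm without responders; under a default Wald analysis this costs power if the placebo rate is low

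*SAP*

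**What the plan says.** SAP 6.3.3 sets one method for all categorical efficacy and health-outcome variables: a logistic model whose only term is treatment. On inference it states: "The p-value and 100(1-alpha)% CI for the odds ratio from the logistic regression model are used for primary statistical inference". The type of test and interval is not given. The same paragraph also plans a Newcombe-Wilson interval for the difference in percentages and, as a secondary analysis, a Fisher p-value.

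The estimand is on another scale. SAP 6.1.1 states: "The primary comparison of interest is the difference in proportion of participants who achieve HiSCR response at Week 16".

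Protocol 9.4.6, under sensitivity analyses, says: "Fisher's exact test may be used as an alternative to logistic regression on the primary endpoint due to the small sample size". No condition is given for when that substitution happens.

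The method reaches beyond the primary endpoint. For the 75% and 90% HiSCR definitions, SAP 6.7.3.1 says: "The same analysis method used for the primary endpoint will be used for these exploratory analyses". For subgroups, SAP 6.10 says: "The subgroup analyses for categorical outcomes will be performed using logistic regression".

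The design figures are "All tests of treatment effects will be conducted at a 2-sided alpha level of 0.05, unless otherwise stated" (SAP 6.3) and "This sample size provides at least 80% power to the primary endpoint of HiSCR response" (Protocol 9.2). The current protocol randomizes 42 v 21; the SAP still shows 34 v 17. The response rates behind the power statement are redacted.

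**The concern.** In an ordinary maximum-likelihood logistic model, an arm with no responders makes the odds ratio infinite and its standard error meaningless. The default Wald p-value then cannot be significant, however many responders the other arm has. With one or two placebo responders the Wald test is defined but conservative. A low placebo rate is therefore the setting in which the named primary inference works worst.

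Other rules push the analysed rates down. Missing HiSCR counts as nonresponse (SAP 6.4), early discontinuation and prohibited medication count against response (SAP 6.1.1), and only about 45 of 63 randomized participants are expected to complete 16 weeks (Protocol 9.2). The stricter HiSCR definitions make low counts more likely still.

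Leaving the test unnamed also matters. Wald, likelihood-ratio and Fisher p-values can differ in significance at this size, and only a loose option governs the choice. By contrast, SAP 6.3.3 gives the repeated-measures model an ordered list of fallback covariance structures if it does not converge; the logistic model has no equivalent.

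**Working it through.** **Inputs.** Two-sided alpha 0.05 (SAP 6.3); 42 v 21 (Protocol 9.2) and 34 v 17 (SAP 6.2); treatment-only logistic model (SAP 6.3.3). Response rates are assumed over a range. The default Wald test is assumed.

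**The plan's own figure.** The stated power of at least 80% cannot be reproduced without the redacted rates. For orientation, the pooled normal approximation at 42 v 21 gives 80% power for active rates of 42.9%, 49.7%, 55.8%, 61.3% and 66.5% against placebo rates of 10%, 15%, 20%, 25% and 30%.

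**Chance of no placebo responders**, (1 − p)^n:

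| Placebo rate | n = 21 | n = 17 |
|---|---|---|
| 5% | 34.1% | 41.8% |
| 10% | 10.9% | 16.7% |
| 15% | 3.3% | 6.3% |
| 20% | 0.9% | 2.3% |
| 30% | 0.06% | 0.2% |

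If completion were 45/63 = 0.714 in both arms and all noncompleters were nonresponders (an assumption), completer rates of 10%, 20% and 30% would become analysed rates of 7.1%, 14.3% and 21.4%. The chance of 0/21 is then 21.1%, 3.9% and 0.6%.

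**What Wald does with few responders.** With a of 42 active and c of 21 placebo responders, log OR = ln[a(21 − c) / (c(42 − a))] and SE = √[1/a + 1/(42 − a) + 1/c + 1/(21 − c)].
- c = 0: 1/c is infinite, so no value of a can reject. For 15/42 v 0/21 an ordinary fit failed with a singular matrix, while Fisher gives p = 0.0012. Firth adds half a responder and half a nonresponder to each arm in this model, so its odds ratio is finite: (15.5/27.5) / (0.5/21.5) ≈ 24. Firth rejects from 7/42; Fisher and Newcombe from 8/42.
- c = 1: at a = 12, ln 8 / √1.167 = 2.079/1.080 = 1.93, not significant. At a = 13, ln 8.97 / √1.161 = 2.193/1.078 = 2.04, significant. Wald therefore needs 13/42, where Firth, Fisher and Newcombe need 11/42.

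**Power at 42 v 21.** All 43 × 22 tables were enumerated and weighted by binomial probabilities; an empty cell counts as a Wald non-rejection. Firth uses the profile penalized likelihood ratio.

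| Active v placebo | Wald | Firth | Gap (points) |
|---|---|---|---|
| 35% v 5% | 40.9% | 83.2% | 42.3 |
| 40% v 10% | 58.9% | 74.1% | 15.2 |
| 50% v 15% | 76.7% | 81.7% | 5.0 |
| 55.8% v 20% | 77.4% | 80.1% | 2.7 |
| 60% v 25% | 74.4% | 75.6% | 1.2 |
| 65% v 30% | 74.6% | 74.9% | 0.3 |

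At 34 v 17 the gaps are wider: 42.6 v 62.5% (40% v 10%) and 63.7 v 72.2% (50% v 15%).

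**Maximum type I error over common rates.**

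| Test | 42 v 21 | 34 v 17 |
|---|---|---|
| Wald | 4.7% | 4.5% |
| Unpenalized likelihood ratio | 7.4% | 7.2% |
| Fisher | 3.6% | 3.7% |
| Boschloo (exact unconditional) | 4.9% | 4.9% |
| Firth, profile likelihood | 5.02% | 4.84% |

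**Agreement with the Newcombe interval.** Wald and Newcombe disagree on significance in 42%, 15% and 5.4% of trials at 35% v 5%, 40% v 10% and 60% v 25%. At 60% v 25% Firth still disagrees in 4.1%. Part of this comes from Newcombe itself, whose implied test has a maximum size of 6.1%.

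**The case against.** The SAP never says Wald; a likelihood-ratio or exact logistic p-value would exist with an empty cell. The protocol foresaw the small-sample problem and permits Fisher's test. Fisher's p-value and the Newcombe-Wilson interval are already to be produced, and both are defined with zero responders. A simple rule using them (Wald, but Fisher when placebo has no responders) would give 74.7% (35% v 5%), 69.8% (40% v 10%), 80.0% (50% v 15%) and 74.6% (60% v 25%), with maximum size 4.7%. Against Firth that leaves 8.5, 4.3, 1.7 and 1.0 points. The large losses also need placebo rates that no unredacted text supports.

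Most of this stands and limits the point. It does not remove it: the supporting results are secondary or optional, nothing says when they take over, and leaving the test open also leaves open a likelihood-ratio p-value with 7.4% size.

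Three stronger readings are tempting and not supported:
- A reader might infer that the planned test inflates false positives. The Wald version does not.
- A reader might infer that power is lost generally at this sample size. From a 25% placebo rate the loss is about 1 point or less.
- A reader might infer that Fisher's test should become primary. At rate pairs with nominal 80% power at 42 v 21, Fisher trails Wald from a 20% placebo rate upward (76.5 v 77.4% at 20%, 72.9 v 78.5% at 30%).

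**Conclusion.** The point holds as a gap in specification with a conditional cost. SAP 6.3.3 makes the odds-ratio p-value and interval decisive without naming the test or giving a binding rule for an empty cell. If the default Wald analysis is what was meant, the power loss against Firth at 42 v 21 is 15 points or more at placebo rates of about 10% or less, 5 points at 15%, 2.7 at 20%, and about 1 or less from 25%.

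This rests on the Wald assumption and on assumed response rates. Because the planning rates are redacted, the documents do not show where in this range the trial lies, and they do not support saying that the primary inference will fail. Firth was at least as powerful as Wald at every rate pair in the table, and its maximum size is 5.0%. It reduces but does not remove disagreement with the Newcombe interval. Subgroup-interaction models were not computed, so no size is claimed for them.

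**What to change.** Before unblinding, add to SAP 6.3.3 that the p-value and confidence interval for the odds ratio, for the primary endpoint and the other treatment-only logistic models, come from Firth penalized likelihood with profile-likelihood inference. An exact unconditional test such as Boschloo's is an acceptable alternative for the p-value (maximum size 4.9%). Keep the Newcombe-Wilson interval for the difference, which is on the estimand's scale, and Fisher's test, both as supporting results. Align Protocol 9.4.6, or state in the SAP that Fisher's test does not replace the primary test, so that the choice is not open once data are seen.

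The cost is a sentence or two in the SAP and a standard software option. The downside is slight shrinkage of the odds ratio towards no effect.

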### 6.7.2. Secondary Endpoints

Secondary comparisons of interest are the mean change from baseline to Week 16 for

- total number of abscesses and inflammatory nodules (AN count), and
- Skin Pain – HS NRS.

The Skin Pain – HS Numeric Rating Scale (NRS) is a patient-administered, single-question, 11-point horizontal scale anchored at 0 and 10, with 0 representing “no pain” and 10 representing “pain as bad as I can imagine.” The recall period is 7 days.

An analysis of covariance (ANCOVA) model with proper link function will be used for analysis of these secondary endpoints on the mITT and PPS population. The AN count is a count data and we will use log transformation as the link function.

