### 6.7.3.3. Modified Sartorius Score (mSS)

The mean percent change from baseline to Week 16 for the total modified Sartorius Score (mSS) will be summarized by treatment group and assessed using MMRM methods.

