### 6.7.3.5. Patient-Reported Outcomes

Categorical variables will be analyzed using logistic regression analyses, whereas the mixed-effects model of repeated measures (MMRM) will be the method of analysis for continuous endpoints. The analyses will be based on the mITT population unless otherwise specified.

The following continuous endpoints from patient-reported outcomes will be assessed:

- Mean change from baseline to Week 16 on the Dermatology Life Quality Index (DLQI)
- Mean change from baseline to Week 16 on the Drainage Numeric Rating Scale
- Mean change from baseline to Week 16 on the Smell Numeric Rating Scale

The following categorical endpoints from patient-reported outcomes will be assessed:

- Proportion of patients responding “no symptoms” on the Patient Global Impression of Severity – 7 Days (Hidradenitis Suppurativa)
- Proportion of patients responding “much better” on the Patient Global Impression of Change – 7 Days (Hidradenitis Suppurativa)
- Proportion of patients responding “much better” or “a little better” on the Patient Global Impression of Change – 7 Days (Hidradenitis Suppurativa)
- Proportion of patients with baseline skin pain NRS $\geq$ 3 having a decrease in skin pain NRS $\geq$  30%
- Proportion of patients with baseline drainage NRS $\geq$ 3 having a decrease in drainage NRS $\geq$  30%
- Proportion of patients with baseline smell NRS $\geq$ 3 having a decrease in smell NRS $\geq$  30%

For patients who meet the criteria at baseline for the presence of inflammatory back pain (IBP), the following endpoints will be assessed using ANCOVA:

- Mean change from baseline to Week 16 on the weekly spinal pain numeric rating scale
- Mean change from baseline to Week 16 on the weekly nightly spinal pain numeric rating scale.

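### SAP 6.3.3 places heterogeneous Toeplitz last in the MMRM fallback, behind two special cases of itself, so it is practically unreachable; the effect is modest and falls mainly on exploratory endpoints

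*SAP*

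**What the plan says.** SAP Section 6.3.3 sets the general rule for continuous outcomes: "The main analysis for all continuous efficacy and health outcomes variables will use mixed model repeated measures (MMRM) analysis". The covariance comes first as "An unstructured (co)variance structure will be used to model the between- and within-patient errors", and the fallback follows: "If this analysis fails to converge, the heterogeneous autoregressive [ARH(1)], followed by the heterogeneous compound symmetry (CSH), followed by the heterogeneous Toeplitz (TOEPH". Degrees of freedom are by Kenward-Roger: "The Kenward-Roger method will be used to estimate the degrees of freedom". No reason is given for the order.

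The endpoint sections narrow the scope.

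- **MMRM:** Section 6.7.3.3 says mSS "will be summarized by treatment group and assessed using MMRM methods", and 6.7.3.4 does the same for IHS4. For the patient-reported outcomes in 6.7.3.5 (DLQI, drainage NRS, smell NRS), "the mixed-effects model of repeated measures (MMRM) will be the method of analysis for continuous" endpoints.
- **ANCOVA:** For the two secondary endpoints, AN count and skin pain, Section 6.7.2 says "An analysis of covariance (ANCOVA) model with proper link function will be used for analysis of these secondary endpoints", in line with Protocol Section 9.4.3. Lesion counts (6.7.3.2) and spinal pain (6.7.3.5) are also assigned to ANCOVA.
- **Logistic regression:** The primary endpoint, HiSCR, is in 6.7.1, with missing values counted as nonresponse (6.4).

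On dropout, Protocol Section 9.2 plans about 63 randomized and states: "For all randomized patients, approximately 45 patients are expected to complete" the 16-week period.

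**The concern.** A fallback list normally gives up flexibility in steps. This one drops straight to the most restrictive structures and offers the intermediate one last. ARH(1) and CSH are both contained in TOEPH, so data on which both of them fail to converge are unlikely to support the larger model. The third fallback is therefore close to dead text.

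The order can matter because MMRM handles missing-at-random dropout through the fitted covariance. ARH(1) makes correlation decay geometrically with time. If patients differ in a lasting way beyond what baseline explains, ARH(1) gives early values too little weight and pulls the implied Week 16 values of dropouts too quickly towards the model mean. When that error differs between arms it does not cancel in the treatment contrast. The amendment rationale in the protocol says that discontinuation was higher than expected, so the handling of dropout deserves care here.

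**Working it through.** **Figure in the plan.** The documents give no number for the fallback, so there is none to reproduce. The stated power of at least 80% concerns HiSCR only, its response rates are redacted, and this point does not depend on it.

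**Step 1: visits.** From the schedule in Protocol Section 1.3, lesion assessments and the drainage and smell NRS are taken at Weeks 2, 4, ..., 16, which gives T = 8 post-baseline visits. DLQI is taken at Weeks 4, 8, 12 and 16, so T = 4. This assumes that the Week 16 MMRM uses Period 1 visits only. The visits are evenly spaced, which suits a Toeplitz structure.

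**Step 2: parameter counts.**

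| Structure | Formula | T = 8 | T = 4 (DLQI) |
|---|---|---|---|
| Unstructured | T(T+1)/2 | 36 | 10 |
| TOEPH | T + (T−1) | 15 | 7 |
| ARH(1) | T + 1 | 9 | 5 |
| CSH | T + 1 | 9 | 5 |

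**Step 3: nesting.** All three fallbacks have covariance σᵢσⱼρ(k) at lag k = |i−j|. TOEPH leaves each ρ(k) free. ARH(1) sets ρ(k) = ρᵏ, and CSH sets ρ(k) = ρ. Both are therefore special cases of TOEPH, and neither contains the other. As an illustration of ARH(1) decay, a lag-1 correlation of 0.7 implies 0.7⁷ = 0.08 between Weeks 2 and 16.

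**Step 4: dropout.** Protocol: (63 − 45)/63 = 18/63 = 28.6%. SAP Section 6.2 still has 51 randomized, giving (51 − 45)/51 = 6/51 = 11.8%. The protocol figure is used below.

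**Step 5: large-sample bias without baseline covariates.** Assumptions: 8 visits, 2:1 allocation, SD 1, and monotone dropout with hazard depending on the last observed value, calibrated to 18/63. The true correlations and the 0.5 SD effect are assumed; the documents give none.

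| True correlation | Dropout rule | True effect | ARH(1) bias (SD) |
|---|---|---|---|
| ARH(1) | all rules tried | 0 or 0.5 SD | 0.000 to 0.001 |
| Not ARH(1) | same in both arms | none | 0.002 to 0.003 |
| Not ARH(1) | same in both arms | 0.5 SD | 0.013 to 0.039, towards the null |
| Not ARH(1) | response-related in placebo only | 0 or 0.5 SD | 0.093 to 0.142 |

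TOEPH bias was 0.000 to 0.002 SD in every scenario, but every assumed truth was of Toeplitz type. CSH is not safe either: with a true ARH(1) correlation and placebo-only dropout its bias was 0.062 SD, in the opposite direction.

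**Step 6: with the SAP's baseline and baseline-by-visit terms.** These remove part of the lasting difference between patients. If all visits including baseline share a correlation c, the correlation given baseline is (c − c²)/(1 − c²) = c/(1+c); for c = 0.6 that is 0.6/1.6 = 0.375. A large-sample check with these terms and about 29% dropout gave:

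| Dropout rule | ARH(1) bias (SD) | TOEPH bias (SD) |
|---|---|---|
| Response-related in placebo only | 0.03 to 0.06 | 0.02 or less |
| Response-related, opposite directions by arm | 0.06 to 0.13 | 0.02 or less |
| Same in both arms | near zero | near zero |

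**Step 7: scale.** At 42:21, without baseline terms, the standard error of the Week 16 contrast was about 0.29 to 0.31 SD under either structure. Against 0.30 SD, the Step 6 range is 0.03/0.30 = 0.1 to 0.13/0.30 = 0.4 standard errors. A smaller standard error after baseline adjustment would raise these ratios somewhat.

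**The case against.** The strongest case on the other side has five parts.

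- **Scope.** The general MMRM sentence in 6.3.3 is overridden, endpoint by endpoint, by ANCOVA for AN count, skin pain, lesion counts and spinal pain, and the primary endpoint is logistic. This stands: the endpoints clearly under MMRM are all exploratory.
- **Trigger.** Nothing happens unless the unstructured model fails, and the documents give no reason to expect that. In a check with 63 patients, 8 visits, about 29% response-related dropout and baseline-by-visit adjustment, the unstructured fit converged in 800 of 800 simulated trials over four assumed correlation patterns. That check used normal data, left out the region and severity terms, and did not use the sponsor's software. It makes the fallback unlikely but does not make its order irrelevant.
- **Mechanism.** A reader might infer that response-related dropout by itself biases the Week 16 contrast under ARH(1). It does not. With one dropout rule for both arms and no treatment effect the errors cancel, and with a true ARH(1) correlation there is no error to cancel. The documents report more discontinuation than expected but no cause and no pattern by arm.
- **Missing data.** SAP Section 6.4 permits last-observation or other imputation for continuous endpoints. If values are imputed before the MMRM, the argument changes.
- **Order of CSH and ARH(1).** Each has T + 1 parameters and neither contains the other, so ranking them is a matter of preference. This stands too, and the fix leaves that order open.

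What survives is the drafting defect: the most flexible fallback sits where it will practically never be used.

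**Conclusion.** The order in SAP 6.3.3 is the wrong way round for TOEPH; that follows from the text and the nesting alone. The consequence is conditional. Three things must hold together: the unstructured model fails, the true correlation is not close to ARH(1), and dropout acts differently in the two arms. The MMRM Week 16 contrast may then be biased by roughly 0.03 to 0.13 SD with ARH(1), against about 0.02 SD or less with TOEPH. These sizes rest on assumed correlations and dropout mechanisms with about 29% dropout. The documents fix neither size nor direction, and the simulations do not show that TOEPH is unbiased under every structure.

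The endpoints concerned are mSS, IHS4, DLQI, drainage NRS and smell NRS. AN count and skin pain are touched only if 6.3.3 prevails over 6.7.2. HiSCR is not affected.

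A reader might also infer a loss of power for the trial. The documents do not support that: power is stated for HiSCR only, and the standard error hardly differs between the two structures. Priority is minor.

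**What to change.** In SAP Section 6.3.3, reorder the fallback so that TOEPH is tried immediately after the unstructured model. CSH and ARH(1) follow in either order, provided that the order is prespecified. Use the first structure that converges, with Kenward-Roger throughout as now.

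The cost is one sentence of SAP text before unblinding. Nothing is given up: if TOEPH fails, the analysis moves on to the simpler structures already listed, and the simulated standard errors show no material loss of precision from fitting TOEPH first.

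The same revision should state whether 6.3.3 or 6.7.2 governs AN count and skin pain, since that decides whether this point reaches the secondary endpoints.
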